4.3. Withdrawal Criteria

4.3.1. Before First Treatment Administration

Before the first treatment administration, inclusion/exclusion criteria will govern the subjects to be dosed. Subjects who have been screened but who have not been randomized into the study may be re-screened once for participation if approved by the medical monitor and Sponsor e.g. subject has upper respiratory tract infection or has a positive poppy seed drug test at the screening visit. Subjects who do not meet the awake cough count criteria at screening (Awake Cough Count of > 10 per hour) cannot be re-screened.

Sponsor Project Nº CL-5937-02

Awake cough count results must not be rounded. Subjects may not be randomized into the study more than once.

Subjects who report a taste disturbance at Day 0 should not be randomized and should not be re-screened.

4.3.2. After First Treatment Administration

Subjects may, at any time, voluntarily withdraw from the study or be removed from the study at the discretion of the Investigator or Sponsor.

If such withdrawal occurs, or if the subject fails to return for visits, the Investigator should determine the primary reason for a subject's premature withdrawal from the study and record the reason in the subject's study documents.

Attempts should be made to have such subjects complete the EOS/ET assessments. EOS/ET assessments should be performed as soon as possible after the last study treatment administration.

The blind may be broken only in emergency situations, where knowledge of the treatment that the subject received is necessary for safety management (Section 5.2.4).

Details of reasons for removal of subjects will be recorded, reported to the Sponsor and documented in the clinical study report.

For subjects who are lost to follow-up (i.e. those subjects whose status is unclear because they fail to appear for study visits without stating an intention to withdraw), the investigator should show "due diligence" by documenting in the source documents steps taken to contact the subject, e.g. dates of telephone calls, registered letters, etc.

4.3.3. Individual Subject Stopping Rules

Possible reasons for discontinuation from the study are:

- The investigator may decide to terminate a subject's participation in the study for safety or administrative reasons e.g. AE, a clinically significant laboratory value, or other medical condition or situation such that continued participation in the study would not be in the best interest of the subject. Appropriate medical measures are to be taken accordingly, and the Sponsor or Sponsor designee is to be notified immediately.
- Subject may be discontinued due to poor study treatment compliance (Section 5.2.6).
- A female subject has a confirmed pregnancy, or, in the case of a male subject, his female partner becomes pregnant.
- At any time during the study a subject may decide to end his/her participation in the study.
- The Investigator or the Sponsor, for any reason, terminates the study.

4.3.4. Liver Function Stopping Criteria

Stopping criteria for an individual subject, after a re-test if needed:

- Any subjects with ALT or AST > 8x ULN
- Any subjects with ALT or AST > 3x ULN and total bilirubin > 2x ULN or INR > 1.5
- Any subjects with ALT or AST > 3x ULN with the appearance of fatigue, nausea, vomiting, right upper quadrant pain or tenderness, fever, rash, and/or eosinophilia (>5%)

Sponsor Project № CL-5937-02

Note: alternative causes (acute viral hepatitis, hepatobiliary disorders, alcoholic and autoimmune hepatitis, NASH, cardiovascular causes and concomitant treatments that might be responsible for the injury) will have to be eliminated prior to subject discontinuation.

Stopping criteria for entire study:

The study will be temporarily halted if ≥ 1 subject has an increase in ALT or AST > 3x ULN associated with elevation in total bilirubin > 2x ULN and no evidence of obstruction, such as elevated ALP typical of gall bladder or bile duct disease, or malignancy, or impaired glucuronidation capacity caused by genetic (Gilbert syndrome) or pharmacologic (treatment with atazanavir or other drugs) factors, with no other explanation (viral hepatitis, alcoholic or autoimmune hepatitis, other hepatotoxic drugs). If underlying causes are identified, the study may continue if the safety review is supportive. The study will be stopped if no underlying causes are identified.

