5.2. Investigational Product Management

5.2.1. Packaging, Labelling and Dispensing

The sponsor will be responsible for ensuring that the investigational product and placebo are manufactured in accordance with applicable current Good Manufacturing Practice (cGMP) regulations and requirements.

^{*} Alginate therapy is accepted but should not be taken concomitantly with study medication which should be taken an hour before or 2 hours after alginate.

[§] Stopping chronic corticosteroid use should be approved and supervised by a physician before stopping

Sponsor Project Nº CL-5937-02

The investigational product and placebo will be labelled according to the requirements of local law and legislation.

BLU-5937 tablets or placebo will be provided for Period 1 and 2 by in treatment kits containing 4 opaque HDPE bottles per kit for each period. Each bottle represents one of 4 dose levels (25, 50, 100, 200 mg BID). The investigational product will be administered as 25 mg tablets (for the 25, 50, 100 mg BID dose levels) or 200 mg tablets (for the 200 mg BID dose level) or matching placebos. BID dosing means every 12 hours, +/- approximately 1 hour. Each bottle will contain sufficient medication to cover the 4 -day treatment duration plus 1 extra day (total 5 days). When a new dose is dispensed it is to be started the following morning after the cough recording device is removed. There is no flexibility in visit window for Treatment visits; each dose is to be taken for 4 days.

Table:	3.	Treatment Kit Dispensing
I UDIC	•	Treatment the Dispensing

Study DayNo.#	BLU-5937 Dose*/Placebo	
Period 1 (treatment kit dispensing)		
Days 1-4	25 mg (1 tablet) BID or placebo	
Days 5-8	50 mg (2 tablets) BID or placebo	
Days 9-12	100 mg (4 tablets) BID or placebo	
Days 13-16	200 mg (1 tablet) BID or placebo	
Washout 10-14 days		
Day 17-30	No treatment	
Period 2 (treatment kit dispensing)		
Days 31-34	25 mg (1 tablet) BID or placebo	
Days 35-38	50 mg (2 tablets) BID or placebo	
Days 39-42	100 mg (4 tablets) BID or placebo	
Days 43-46	200 mg (1 tablet) BID or placebo	

^{*}Product can be administered without regard to meals

Once it is confirmed the subject has provided written consent and meets all the inclusion and none of the exclusion criteria the investigational product and placebo will be dispensed to individual subjects as per the randomization schedule.

Further details regarding packaging, labelling and accountability can be found in the pharmacy manual.

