11. ADMINISTRATIVE PROCEDURES

11.1. Adherence to Protocol

Excluding an emergency situation in which proper treatment is required for the protection, safety and well-being of the study subjects, the study will be conducted as described in the approved protocol and performed according to ICH GCP, local Regulations and guidelines. Any deviation from the protocol will be recorded and explained. Subject-related Protocol Deviation (PDs) will be logged in the by each site. Lists per site will be printed & signed by their Principal Investigator.

If amendments to the protocol and/or amendments or revisions to the ICF are required, the modifications will be documented and submitted to an IEC/IRB for approval.

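### Section 4.3.4 makes liver-related discontinuation wait for re-test and work-up, with no required dose hold and no time limit in the meantime

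*Combined protocol and SAP*

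**What the plan says.** Protocol section 4.3.4 (Liver Function Stopping Criteria) opens with "Stopping criteria for an individual subject, after a re-test if needed". Three criteria follow:

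- ALT or AST above 8x ULN;
- ALT or AST above 3x ULN with total bilirubin above 2x ULN or INR above 1.5;
- ALT or AST above 3x ULN with listed symptoms or eosinophilia.

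A Note covers all three. It names viral and autoimmune hepatitis, hepatobiliary disease, NASH, cardiovascular causes and concomitant treatments, and says that such causes "will have to be eliminated prior to subject discontinuation".

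The same section has a rule for the whole study, beginning "The study will be temporarily halted if". Its trigger is at least one subject with ALT or AST above 3x ULN and bilirubin above 2x ULN, without obstruction or another explanation.

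On dosing, 5.2.1 states "There is no flexibility in visit window for Treatment visits; each dose is to be taken for 4 days" and "When a new dose is dispensed it is to be started the following morning after the cough recording device is removed". Section 5.2.6 asks that dosage and timing stay on schedule and defines noncompliance as any departure from 100% of prescribed medication between visits.

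Three other places allow a subject to be stopped. Under 4.3.3 the investigator may end participation "for safety or administrative reasons e.g. AE, a clinically significant laboratory value". Under 4.3.2 a subject may "be removed from the study at the discretion of the Investigator or Sponsor". Section 11.1 opens with "Excluding an emergency situation in which proper treatment is required for the protection, safety and well-being of the study subjects".

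**The concern.** The individual criteria are the protocol's only liver-specific rule for stopping one subject. Such a rule is useful because reaching the threshold is itself meant to bring action. Here the threshold starts an inquiry, and discontinuation waits for its result. The text does not say what happens to dosing meanwhile, while a forced-escalation schedule continues by default. What is at stake is further exposure, possibly at higher doses, in a subject whose liver tests have already reached a threshold the protocol regards as serious. Whether that is prevented depends on someone choosing to use a permissive power.

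**Working it through.** No figure in the plan bears on this point, so the check compares the texts and then sets bounds from the schedule.

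**1. Sequence under 4.3.4.** A threshold value is seen; it is re-tested if needed (no interval given); alternative causes are eliminated (no limit given); the subject is discontinued. No instruction on dosing appears between the first and last steps.

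**2. Is a hold supplied elsewhere?**

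| Place | What it provides | Mandatory hold for one subject? |
|---|---|---|
| 4.3.2 | Removal at discretion | No |
| 4.3.3 | Investigator may end participation | No |
| 11.1 | Emergency exception to following the protocol | No |
| 6.1.5 | Investigator judges each abnormal value; clinically significant post-dose values become AEs | No |
| 4.3.4, study rule | Temporary halt of the study | Not subject-level; bilirubin-based trigger only |
| 5.2.1, 5.2.6 | Fixed 4-day levels; compliance definition | No, and no safety exception stated |

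The routes in 4.3.2 and 4.3.3 end participation; they do not describe a pause.

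**3. Reach of the study-wide halt.** It requires bilirubin above 2x ULN. A subject above 8x ULN, or above 3x ULN with raised INR or symptoms, falls outside it unless bilirubin is also raised. Where bilirubin is raised, the halt still depends on there being no obstruction or other explanation.

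**4. What the schedule can produce.** Inputs are Table 3 and section 5.2.1 (level starts) and Table 4 (LFT days). Days are for Period 1; add 30 for Period 2 with a 14-day washout.

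Level starts after the first are Day 5 (50 mg BID), Day 9 (100 mg BID) and Day 13 (200 mg BID). Each doubles the last: 50/25 = 100/50 = 200/100 = 2. End-of-level draws fall on Days 4, 8, 12 and 16. Offset = start day minus draw day:

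| Draw | Offsets of later level starts (days) |
|---|---|
| Day 4 | 5−4 = 1, 9−4 = 5, 13−4 = 9 |
| Day 8 | 9−8 = 1, 13−8 = 5 |
| Day 12 | 13−12 = 1 |
| Day 16 | none |

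Let R be the days from the draw until the first threshold result is known, and E the days until re-test and work-up are both finished. Escalations within the wait = number of offsets s with R < s < E. The documents give neither R nor E. The bounds, in the order of the four draws, are:

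- R under 1 day: 0 to 3, 0 to 2, 0 to 1, 0.
- R from 1 to under 5 days: 0 to 2, 0 to 1, 0, 0.
- R from 5 to under 9 days: 0 to 1, 0, 0, 0.
- R of 9 days or more: 0 throughout.

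Two assumed cases show the spread. With R = 2 and E = 8.5 the counts are 1, 1, 0, 0. With R = 2 and E = 4 they are all 0.

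Samples go to a central laboratory unless otherwise specified (6.1.5). If results take more than a day, the doubling at offset 1 happens before anyone knows of the abnormality, and no hold rule could prevent it. These counts concern the BLU-5937 period only.

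**The case against.** The Note conditions discontinuation, which 4.3.3 uses in the sense of leaving the study. It is silent about pausing drug: it neither requires dosing during the work-up nor forbids a hold. Asking for a cause before permanent removal is defensible. The investigator sees every abnormal value under 6.1.5, can end participation at once for a clinically significant one, and can act in an emergency. Section 5.2.6 concerns compliance and does not bar a safety hold. A Safety Plan (7.5, 7.6), SRC review (8.13) and a Laboratory Manual (6.1.5) are mentioned but not available here, and text is absent under 1.9 and 1.9.1; any of these could contain a hold.

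Most of this stands, and it limits the point. What it does not supply is a mandatory interruption tied to the liver thresholds. The discretionary powers are permissive, do not refer to those thresholds, and sit beside a Note that tells the investigator to complete the work-up first. Section 4.3.4 refers to none of the unseen material for individual stopping.

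**Conclusion.** The point holds in a limited form. On the readable text, discontinuation of a subject who reaches an individual liver threshold waits for any re-test and for the work-up, with no required hold and no time limit. Interruption in that interval is discretionary, except where the narrower study-wide halt applies. This should be changed, but it is a gap in one rule and not an absence of protection.

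Three stronger readings are tempting and unsupported:

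- A reader might infer that the protocol forces dosing to continue. It does not; 4.3.2, 4.3.3 and 11.1 all permit stopping.
- A reader might take the escalation ceiling of 3 as the expected exposure. It is only a limit set by the schedule. The actual number cannot be computed without turnaround times and may be zero.
- A reader might say that every threshold without bilirubin in its definition escapes the study-wide halt. The presentations overlap: a subject above 8x ULN who also has bilirubin above 2x ULN and no other explanation meets it.

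The conclusion assumes that no hold is set out in the material not available here.

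**What to change.** Amend both the header and the Note in 4.3.4. The header matters because it applies the criteria only after a re-test; a hold that starts when a criterion is met could leave the re-test interval uncovered. Suggested wording:

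*Study drug is held, with no further dosing or escalation, from the first result that reaches any threshold below, pending any re-test and the search for alternative causes; the outcome decides only between permanent discontinuation and resumption.*

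State whether a held subject may resume, and at which level. This also matters for the analysis: 8.4.1 compares each dose with placebo at the matching assessment visit, so a subject who resumes at a lower level would have visit and dose out of step. List the hold as an exception in 5.2.1 and 5.2.6 so that it is not counted as noncompliance.

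The change is to wording and leaves the sample size alone. Its cost is that held subjects may miss some dose-level cough assessments, which become missing data in the primary model.

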4.4. Prohibited Medications and non-pharmacological Therapies / Washout

Subjects will be instructed to notify the study site about any new medications taken after the start of the study treatment. Subjects will be asked at each visit if any medications have been taken since their last visit. All medications and significant non-drug therapies (including physical therapy and blood transfusions) administered after the subject has received the study treatment must be listed in the subject CRF/source documents. The drug name and dose taken will be recorded in the CRF/source documents. Table 2 below outlines all the prohibited medications and non-pharmacological therapies and the washout periods, where applicable before the subject can be enrolled. Investigators are encouraged to contact the study medical monitor if they need to discuss any of the below for advice.

Table 2. Prohibited Medications and non-pharmacological Therapies / Washout Period

Medication	Washout Period / Restrictions					
Antitussive Medications / Therapy						
Including but not limited to: dextromethorphan, opioids	Not permitted within 1 week of baseline and prohibited throughout					
Gabapentin/pregabalin/baclofen/tricyclics	Should be tapered off safely before stopping and are not permitted within 4 weeks of baseline and prohibited throughout					
For Underlying Respiratory Disease / Other Clinical Indications						
Chronic systemic corticosteroid use e.g. Prednisone	Not permitted within 4 weeks of screening and prohibited throughout [§]					
Inhaled steroids and antihistamines	Stable dose for at least 4 weeks prior to screening visit and throughout the study					
GERD medications e.g. proton pump inhibitors or anti-reflux medications. See exception *	Stable doses for at least 8 weeks prior to screening visit and throughout the study					

Sponsor Project Nº CL-5937-02

Neuromodulators e.g. Gabapentin / pregabalin, baclofen, amitriptyline and other tricyclics taken for another clinical indication (not for cough)	Stable dose for at least 8 weeks prior to screening visit and throughout the study
ACE-inhibitor therapy	Not permitted within 12 weeks of screening or throughout the study
Investigational drugs (including P2X3 antagonist)	Not permitted within 60 days of the first dose of study medication or plans to take another within 30 days of study completion
Beta blockers, NSAIDs, and aspirincontaining products	Prohibited if any previous history of bronchospasm with these products
Biologics	Not permitted within 60 days of the first dose of study medication or plans to take another within 30 days of study completion
Physio / Physical / Speech and language Therapy	Only permitted if they have completed a course of the therapy and it will be stable from screening and throughout the study

[#] Please contact the Medical Monitor

to discuss any case

5. STUDY TREATMENTS

5.1. Investigational Product and Placebo

All doses of the investigational product and placebo will be provided by the sponsor.

5.1.1. BLU-5937 tablets

BLU-5937 (drug product) is manufactured by be provided as 25 mg and 200 mg tablets.

5.1.2. Placebo

Placebo tablets (25 mg and 200 mg) matched to Sponsor's BLU-5937 investigational product manufactured by will be supplied. The excipients in the placebo formulation are identical to the excipients as BLU-5937.

5.2. Investigational Product Management

5.2.1. Packaging, Labelling and Dispensing

The sponsor will be responsible for ensuring that the investigational product and placebo are manufactured in accordance with applicable current Good Manufacturing Practice (cGMP) regulations and requirements.

^{*} Alginate therapy is accepted but should not be taken concomitantly with study medication which should be taken an hour before or 2 hours after alginate.

[§] Stopping chronic corticosteroid use should be approved and supervised by a physician before stopping

Sponsor Project Nº CL-5937-02

The investigational product and placebo will be labelled according to the requirements of local law and legislation.

BLU-5937 tablets or placebo will be provided for Period 1 and 2 by in treatment kits containing 4 opaque HDPE bottles per kit for each period. Each bottle represents one of 4 dose levels (25, 50, 100, 200 mg BID). The investigational product will be administered as 25 mg tablets (for the 25, 50, 100 mg BID dose levels) or 200 mg tablets (for the 200 mg BID dose level) or matching placebos. BID dosing means every 12 hours, +/- approximately 1 hour. Each bottle will contain sufficient medication to cover the 4 -day treatment duration plus 1 extra day (total 5 days). When a new dose is dispensed it is to be started the following morning after the cough recording device is removed. There is no flexibility in visit window for Treatment visits; each dose is to be taken for 4 days.

Table:	3.	Treatment Kit Dispensing
I UDIC	•	Treatment the Dispensing

Study DayNo.#	BLU-5937 Dose*/Placebo	
Period 1 (treatment kit dispensing)		
Days 1-4	25 mg (1 tablet) BID or placebo	
Days 5-8	50 mg (2 tablets) BID or placebo	
Days 9-12	100 mg (4 tablets) BID or placebo	
Days 13-16	200 mg (1 tablet) BID or placebo	
Washout 10-14 days		
Day 17-30	No treatment	
Period 2 (treatment kit dispensing)		
Days 31-34	25 mg (1 tablet) BID or placebo	
Days 35-38	50 mg (2 tablets) BID or placebo	
Days 39-42	100 mg (4 tablets) BID or placebo	
Days 43-46	200 mg (1 tablet) BID or placebo	

^{*}Product can be administered without regard to meals

Once it is confirmed the subject has provided written consent and meets all the inclusion and none of the exclusion criteria the investigational product and placebo will be dispensed to individual subjects as per the randomization schedule.

Further details regarding packaging, labelling and accountability can be found in the pharmacy manual.

5.2.2. Storage and Handling

Investigational product will be shipped from storage directly to site as subject screening commences. Additional kits will be sent once patients are randomized.

Each site will maintain an inventory record of the investigational product and placebo kits received, stored (in a secure restricted area), and dispensed per the randomization schedule and per treatment period.

The investigational product and placebo will be provided to study subjects only.

5.2.3. Method of Assigning Subjects to Treatment Groups

Subjects who have met all the inclusion/exclusion criteria and have read, understood and signed the informed consent form will be randomized 1:1 to treatment sequence (placebo then study drug or study

 $^{^{\#}}$ Day No. in the table assumes a 14-day washout period

Sponsor Project Nº CL-5937-02

drug then placebo). The randomization will be produced by allocated via a web-based electronic data capture system.

5.2.4. Blinding

This study is double-blind.	. Treatment assignments will	ll be blinded to the investiga	itor, subjects and all
clinical and research staff	for the entire study.	supplied and managed by	is the
randomization system in u	se for this study. Blinded ki	t allocation to eligible subje	ects is managed by site
staff via	(randomization & Resupply	r).	

The study blind will be broken upon completion of the clinical study and after the study database has been locked.

During the study, the randomization code must not be broken except in emergency situations where the identification of a subject's study treatment is required by the qualified investigator for further treatment to the subject or to complete a serious adverse event (SAE) report. The qualified investigator (PI or delegated Sub-Investigator) will unblind the subject via the emergency & neither the PI & Sub-Investigator are available, the Medical Monitor can as last resort conduct the unblinding through the limitation in the subject's source files with as few of the site staff unblinded as is clinically reasonable.

